#### Preexisting Condition

A preexisting condition is one that is present at the start of the clinical trial. A preexisting condition will be recorded as an adverse event if the frequency, intensity, or the character of the condition worsens during the study period. At the Screening Visit (V1), any clinically

significant abnormality will be recorded as a preexisting condition in the participant's CRF. Where applicable and at the consent of the participant, additional information from the participant's healthcare provider including medical records, may be requested. Throughout the clinical trial, any new clinically significant findings/abnormalities that meet the definition of an adverse event will also be recorded and documented as an adverse event.

### **Post-study Adverse Event**

At the last scheduled visit, the PI and/or QI should instruct each participant to report any subsequent event(s) that the participant believes might reasonably be related to participation in this clinical trial. The PI and/or QI should notify Health Canada of any death or adverse event (meeting reporting criteria) occurring at any time after a participant has discontinued or terminated participation that may reasonably be related to this clinical trial. Health Canada and Filament Health should also be notified if the PI and/or QI should become aware of the development of cancer or of a congenital anomaly in a subsequently conceived offspring of a participant that was involved in this clinical trial.

### **Abnormal Laboratory Values**

A clinical laboratory abnormality should be documented as an adverse event if any one of the following conditions are met:

- The laboratory abnormality is not otherwise refuted by a repeat test to confirm the abnormality;
- The abnormality suggests a disease and/or organ toxicity;
- The abnormality is of a degree that requires active management (e.g. change of dose, discontinuation of the study intervention, more frequent follow-up assessments, further diagnostic investigation, etc.); or
- Any laboratory abnormalities assessed as being clinically significant by a study physician or qualified individual.

## **8.2 Recording of Adverse Events**

All adverse events occurring during the study period will be recorded. At each contact with the research participant, the research team will seek information on adverse events by specific questioning. Information on all adverse events will be recorded immediately in the participant's CRF and/or legal health record, and recorded in the adverse event log. All adverse events will be assessed by the PI for relatedness, expectedness, seriousness, and severity in relation to the study intervention. All clearly related signs, symptoms, and abnormal diagnostic procedure results should be recorded in the CRF and/or legal health record and assessed by the PI in a timely manner allowing sufficient time to meet required reporting timelines for SAEs and SUADRs (severe unexpected adverse drug reactions) if needed. Adverse events related to the study drug will be reported to Filament Health within 24 hours of the study team becoming aware of the event. These reports should not contain PHI.

## **8.3 Reporting of Serious Adverse Events**

### **8.3.1 Investigator Reporting: Notifying the Sponsor**

There is no sponsor for this study, however Filament Health is the supplier of the psilocybin used in this trial. Filament Health will be sent safety reports on adverse events and serious adverse events within 24hrs of the study team becoming aware of the event. None of these safety reports will contain PHI and all data will be coded.

### **8.3.2 Investigator Reporting: Notifying the REB**

The process for notification to the REB for applicable serious adverse events (SAEs) must be completed as per REB reporting requirements. SAEs and unanticipated events must be recorded and reported to the REB in accordance with the REB's reporting requirements and timelines. Copies of each report and documentation of REB notification and REB receipt/acknowledgement must be kept in the Investigator Study Binder.

### **8.3.3 Sponsor Reporting of SUADRs: Notifying Health Canada**

There is no sponsor for this study, thus the PI/QI is responsible for reporting the safety information to Health Canada as required. The SUADR report must be reported to Health Canada in the following cases:

- Where the ADR is neither fatal nor life-threatening, within 15 days after becoming aware of the information
- Where it is fatal or life-threatening, immediately where possible and, in any event, within 7 days after becoming aware of the information
- And within 8 days after having informed Health Canada of the ADR, submit as complete as possible, a report which includes an assessment of the importance and implication of any findings.

### **8.3.4 Sponsor Reporting of SUADRs: Notifying Sites**

Not applicable.

## **8.4 Reporting of Device Deficiencies**

Not applicable.

## **8.5 Safety Management Plan**

Safety of the participants (including data confidentiality) and the scientific integrity of the project will be ensured by the research team led by the PI. Participant safety will be monitored at each study visit by asking the participant about their experience and about any adverse events from the last study visit. All adverse events will be reviewed by the

study PI and reported to the REB and/or Health Canada in accordance with the regulatory guidelines as outlined by each entity. Adverse events will be recorded and/or reported as outlined in Section 8.2 and 8.3. Safety reports on AEs and SAEs will be provided to Filament Health within 24hrs of the study team becoming aware of the event. In addition, all safety data related to the psilocybin will be provided to Filament Health. None of these safety reports will contain PHI and all data will be coded. The study team will also use a published SBQ-ASC to assess and reduce suicide risk. Participants experiencing a serious adverse event will be immediately withdrawn from the study. In the case of increased suicidality, the study physician will conduct an urgent psychiatric assessment with the participant.

The study investigator and study team will meet regularly to review the accrued data, data confidentiality, recruitment, and participants complaints. Participant confidentiality will be maintained through the use of code numbers to identify all participants. All research records will be kept in a locked file and no participants will be identified in any published report.

Participants may be removed from the study at the discretion of the PI. Reasons for possible withdrawal from the clinical trial are outlined in Section 4.7.1.

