## **3.2 Primary Endpoints**

The primary safety endpoints of the main clinical trial design will be evaluated using standardized adverse events monitoring at all time points. Adverse event monitoring will be prioritized to closely and thoroughly evaluate the acute and sub-acute psychological safety profile. Blood pressure and heart rate will be examined before (V2) and during the psilocybin dosing sessions (V3/V4). Constant observation by therapists will monitor for adverse events during the dosing sessions. An on-call psychiatrist will be available at all times to further assess as needed for acute concerns. The safety endpoint is the number and severity of adverse events reported throughout the duration of the trial.

Feasibility endpoints of the main clinical trial design include the recruitment and retention rates. Dropout rates during three periods will be evaluated, namely: 1) screening period in which the participant undergoes medication tapering and washout; 2) during the acute course of the study intervention; and 3) during the follow-up after the intervention. Throughout all three periods, we will also evaluate adverse events including psychological distress and serious adverse events (e.g., hospitalization, suicide attempt, death).

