#### **4.7.2 Follow-up for Withdrawn Participants**

If a participant withdraws consent, the information that was provided by the participant and recorded by the study team before they withdrew consent will not be destroyed. However, once withdrawn from the clinical trial, no further research procedures or evaluations will be performed, or additional research-specific data collected on the participant. Reasonable effort will be made to obtain permission to document the reason for withdrawal.

Withdrawn participants will be seen clinically by the study investigator to ensure a plan for continued care outside of the study is established. If the participant is interested in hearing about other treatment options, they may be offered a referral to the CBT group for depression and anxiety in autistic adults at CAMH and/or a consultation with a psychiatrist to discuss pharmacotherapy options.

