#### **4.7.3 Early Termination Visit**

If a participant withdraws from the clinical trial, every effort will be made to perform an Early Termination Visit.

Participants that withdraw after the first or second dosing session:

If the participant is willing to attend an Early Termination Visit, the following information will be documented:

- Assessment of new and ongoing AEs;
- Assessment of any complications following the study intervention;
- Documentation of all concomitant medications;

The PI will also ensure the participant is appropriately transitioned/followed for any additional care as required.

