### Prohibited Medications

Participants are to be discontinued from antidepressants and/or antipsychotic medications at least 2 weeks prior to Baseline (V2). Participants on fluoxetine will be tapered off the medication at least 4-weeks prior to Baseline (V2). Additional time may be required as determined by the study investigator. Medications that must be discontinued include the following 2 classes of the Anatomical Therapeutic Chemical (ATC) Classification System: NO5A Antipsychotics & NO6A Antidepressants. Methylphenidate is also included in this list.

These medications should not be re-introduced until after Week 12 (V9) when the study is complete. If the medications are re-introduced, the study investigator must be notified and the medications will be documented in the participant's CRF. Participants who require concomitant medication(s) specifically for the treatment of depression at any time through the duration of the study will be assessed for reasons of resuming their medications.

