#### Adverse Event Collection Period

AEs occurring as of the first study visit (V1) through the final study visit (V9) will be collected. AEs recorded during this period will be followed through to resolution, or until the event is assessed as chronic or stable.

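### Section 8.5 takes a participant out of the whole study after any serious adverse event, and nothing keeps that person on the scheduled safety assessments to V9

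*Protocol*

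**What the plan says.** **The rule.** Protocol Section 8.5 states: "Participants experiencing a serious adverse event will be immediately withdrawn from the study". It is mandatory, speaks of the study rather than the drug, and has no exception for unrelated events or for events after the last dose. Section 4.7.1 lists an AE among the reasons for which an investigator may withdraw someone, if staying would not be in that person's interest. The only circumstance it names in which the investigator will not withdraw a participant is a missed MRI scan.

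**What follows withdrawal.** Section 4.7.2 says that "once withdrawn from the clinical trial, no further research procedures or evaluations will be performed". That clause comes straight after a sentence about withdrawal of consent. The same section provides a clinical visit to arrange care outside the study. Section 4.7.3 adds one Early Termination Visit if the participant is willing. Its content includes "Assessment of new and ongoing AEs", complications and medications, but neither UKU nor SBQ-ASC.

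**What the safety objective needs.** Section 3.2: "The safety endpoint is the number and severity of adverse events reported throughout the duration of the trial". Section 8.1: "AEs occurring as of the first study visit (V1) through the final study visit (V9) will be collected". Section 8.2: "At each contact with the research participant, the research team will seek information on adverse events by specific questioning". The schedule in Section 6.2.1 marks AE review with UKU at every visit from V1 to V9. It marks SBQ-ASC at V1, during tapering, at V2 and at V5 to V9.

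**Medication.** Section 5.6, on antidepressants, antipsychotics and methylphenidate: "These medications should not be re-introduced until after Week 12 (V9) when the study is complete". It also provides for documenting them if they are restarted.

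**The concern.** Stopping a drug and leaving a study are different decisions, and Section 8.5 merges them. For an SAE in week 3, such as an unrelated hospital stay, no dose remains to be stopped. The rule then protects no one from further exposure and only ends scheduled observation.

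Safety is part of the primary objective, and the protocol knows of no earlier psilocybin trial in autistic people. Section 3.2 gives suicide attempt as an example of an SAE. A participant with that event would leave the scheduled suicidality series at the point where its remaining assessments matter most. Because SBQ-ASC is not scheduled at V3 or V4, withdrawal at either dosing visit leaves no scheduled post-dose SBQ-ASC at all. Replacement under Section 4.7.1 restores the number of completers but not the missing record.

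A lesser effect is that withdrawal before V6 also removes the participant from the exploratory clinical-effects set defined in Section 7.2.

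**Working it through.** The protocol gives no figure to reproduce here. The check sets the provisions side by side and then counts visits.

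**Step 1. Does any text keep the participant on the schedule?**

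- Section 4.7.1: discretionary withdrawal for AEs; the stated exception concerns MRI only.
- Section 4.7.2: a clinical hand-over, with no visit schedule.
- Section 4.7.3: one voluntary visit without UKU or SBQ-ASC.
- Section 8.1, collection period: an AE already recorded is followed until resolved, chronic or stable. This concerns the recorded event.
- Section 8.1, post-study events: Health Canada is told of reportable events "occurring at any time after a participant has discontinued or terminated participation that may reasonably be related to this clinical trial". This depends on the investigator learning of them.
- Section 8.5: increased suicidality prompts an urgent psychiatric assessment, with no repeat schedule.

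None of these keeps the V5 to V9 AE/UKU and SBQ-ASC assessments. This holds even if the clause in Section 4.7.2 applies only to withdrawal of consent, because nothing else fills the gap.

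**Step 2. What is lost, by timing of the SAE?**

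Inputs are from Section 6.2.1. AE/UKU visits from the first dose on are V3 to V9, which is 7. Post-dose SBQ-ASC assessments are V5 to V9, which is 5. Nominal days are V3 = -7, V4 = 0, V5 = 1, V6 = 7, V7 = 14, V8 = 28 and V9 = 12 × 7 = 84. Days lost = 84 minus the day of the last visit attended.

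| Last visit attended | AE/UKU lost | SBQ-ASC lost | Days lost |
|---|---|---|---|
| V3 | 6 | 5 | 84 - (-7) = 91 |
| V4 | 5 | 5 | 84 - 0 = 84 |
| V5 | 4 | 4 | 84 - 1 = 83 |
| V6 | 3 | 3 | 84 - 7 = 77 |
| V7 | 2 | 2 | 84 - 14 = 70 |
| V8 | 1 | 1 | 84 - 28 = 56 |

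After V4 the loss is therefore 5 of 7 AE/UKU visits and 5 of 5 post-dose SBQ-ASC assessments. In the V3 row, one of the six lost visits is V4 itself, a dosing visit that would be cancelled anyway. An Early Termination Visit, if it takes place, gives back one AE assessment but no scheduled UKU or SBQ-ASC. The AE/UKU losses are therefore upper limits.

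**Step 3. How many participants?**

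The protocol gives no SAE rate and reports no documented SAEs in the pooled neurotypical trials (Sections 1.4 and 1.6). The relevant risk is that of an SAE after the first dose and before V9. An SAE during tapering costs no post-dose follow-up. With no basis for that risk, I give no probability: the number affected is unknown and may be zero.

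**The case against.** Several points on the other side stand.

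- **No direct contradiction.** A reader might infer that Section 8.5 contradicts the V1 to V9 collection window in Section 8.1 and the endpoint in Section 3.2. It does not. A window for events is not a promise that everyone attends every visit, and early exit shortens follow-up under any withdrawal rule. Section 7.2 includes everyone who enters dosing, so the SAE of a dosed participant is in the safety analysis. The provisions are in tension, no more.
- **The search for new events does not stop.** A reader might infer that it does. Section 8.2 requires AE questioning at every contact, and Section 8.1 follows the recorded event to resolution or stability, so those follow-up contacts also prompt questions about new events. The hand-over, the Early Termination Visit and urgent psychiatric assessment add to this. After a suicide attempt, what goes is the structured score series, not clinical attention.
- **Section 4.7.2 is probably narrower than it looks.** A reader might take it to bar all evaluation of anyone withdrawn. Read that way, it would clash with the Early Termination Visit in Section 4.7.3. It most naturally concerns withdrawal of consent.
- **The rule has a purpose.** Section 8.7 cites Sections 4.7.1 and 8.5 as the stopping rules that help justify having no independent monitoring board. Withdrawal also frees the participant from the medication restriction in Section 5.6. Both purposes can be kept by stopping dosing and permitting treatment.

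These points limit the size of the problem. None of them supplies scheduled UKU or SBQ-ASC assessments after an SAE.

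**Conclusion.** The point holds as a gap in safety follow-up. Section 8.5 requires exit from the whole study after any SAE, Section 4.7.1 treats AE-related withdrawal as discretionary, and no text keeps the participant on the scheduled AE/UKU and SBQ-ASC assessments. Detection of new events is reduced for these participants, not ended.

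Per affected participant, the loss after an SAE at V4 is up to 5 of 7 AE/UKU visits and all 5 post-dose SBQ-ASC assessments. It falls to 1 of each after V8. The counts assume that the visit at or before the event was completed and that Section 8.5 is applied as written. The partial offset assumes that the Early Termination Visit is open to participants whom the investigator withdraws.

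The documents do not support the claim that the sections contradict one another, that all surveillance ceases, or any stated chance that the rule will be triggered. The change is worth making because it is cheap and concerns the primary safety endpoint in those at highest risk.

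**What to change.** - **Section 8.5:** state that an SAE stops any remaining psilocybin dosing, while AE review, UKU and SBQ-ASC continue to V9 unless the participant withdraws consent. If V4 is not given, time this follow-up from the last dose, since the later visits are otherwise counted from V4.
- **Section 4.7.2:** limit the sentence ending research procedures to withdrawal of consent.
- **Section 5.6:** state that a participant kept in follow-up after an SAE may restart antidepressant or antipsychotic treatment as clinically needed, with the treatment recorded.

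With these changes no scheduled post-dose AE/UKU or SBQ-ASC assessment is lost because of the rule, other than the cancelled V4 dosing visit after an SAE at V3.

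The cost is three wording changes and slightly more follow-up work at visits that already exist. Sections 6.1.2.1 and 6.2.1 allow side-effect review and SBQ-ASC at V5 to V9 to be done remotely. The downside is that some symptom data after an SAE will reflect restarted treatment, so the recorded restart dates are needed to interpret them.

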#### Remote Assessment Safety Procedures

All remote assessments will be conducted in a private room. The research team will not require identification from the participant as the research team will already be familiar with the participant and will be able to identify them visually through WebEx. The sessions occurring over WebEx or over the phone will not be recorded. If the assessment requires screen sharing, the individual administering the assessment will ensure that any documents or windows on the desktop containing PHI or personal information will be closed. The individual administering the assessment will also have access to necessary communication technology in order to communicate with relevant research supports or emergency services in case of an emergent situation. When sending invitations for remote assessments or communicating via email, the research team will limit personal information in all emails by avoiding full names or direct identifiers in the subject line of the email or meeting invitation.

## **8.6 Unblinding Procedures**

Not applicable.

## **8.7 Data and Safety Monitoring Board**

According to TCPS 2 (2022) Chapter 11, this study will not have an independent Data and Safety Monitoring Board for the following reasons. First, this study is an open-label and single-site study and does not involve blinded data collection. Second, the possible adverse outcomes of this study are mild to moderate (temporary, non-life-threatening conditions). Third, as noted in Section 4.7.1 and 8.5, this study has clear stopping rules

to ensure the study team can recognize when incidents of harm to participants require a reconsideration of the study design.

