## **4.7 Participant Withdrawal Criteria**

### **4.7.1 When and How to Withdraw Participants**

Participants are free to withdraw from participation in the clinical trial at any time.

An investigator may discontinue or withdraw a participant from the clinical trial for the following reasons:

- Pregnancy or if participants cease effective contraception;
- Significant study intervention non-compliance;
- If any adverse event (AE), laboratory abnormality, or other medical condition or situation occurs such that continued participation in the clinical trial would not be in the best interest of the participant; or
- Disease progression which requires discontinuation of the study intervention;
- If the participant meets an exclusion criterion (either newly developed or not previously recognized) that precludes further study participation.

Notably, even if participants cannot complete a post-treatment brain MRI scan (V5) of *the main clinical trial design* or cannot complete any of brain MRI scans of *the optional dense sampling brain MRI data collection* (either for the personal reasons or for an exclusion criterion for the MRI scan), they will not be discontinued/withdrawn from the trial by an investigator.

The reason for participant discontinuation or withdrawal from the study will be recorded within the participant's research record, and/or health record at CAMH.

Participants that are withdrawn from the study will be replaced using the same recruitment methods as outlined in Section 4.2: Participant Recruitment and Screening. The aim is to have 20 participants who complete the study.

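### The waiver of an independent safety board in 8.7 relies on stopping rules that 4.7.1 and 8.5 do not contain; 9.1, the only trial-level provision, fixes no trigger and is not cited

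*Protocol*

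**What the plan says.** Section 8.7 of the protocol explains why there is no independent Data and Safety Monitoring Board. It gives three reasons: the trial is open-label and single-site; "the possible adverse outcomes of this study are mild to moderate (temporary, non-life-threatening conditions"); and "as noted in Section 4.7.1 and 8.5, this study has clear stopping rules", which are there "to ensure the study team can recognize when incidents of harm to participants require a reconsideration of the study design". That last purpose concerns the trial as a whole.

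The two cited sections read as follows.

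- **4.7.1** opens with "An investigator may discontinue or withdraw a participant from the clinical trial for the following reasons" and lists five reasons. It adds that "Participants that are withdrawn from the study will be replaced", with the aim of 20 completers.
- **8.5** states that "Participants experiencing a serious adverse event will be immediately withdrawn from the study", calls for an urgent psychiatric assessment when suicidality increases, and lets the PI remove participants. It also provides that AEs are reviewed by the "study PI and reported to the REB and/or Health Canada in accordance with the regulatory guidelines", and that "The study investigator and study team will meet regularly to review the accrued data".

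Suspension or termination of the trial appears only in 9.1. That section permits it for sufficient cause and lists grounds such as a PI, funder or REB decision, futility, or a review of related and unexpected serious events. Section 8.7 does not refer to it.

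**The concern.** An ethics board reading 8.7 is told that defined rules stand in for an independent board. If the named sections only remove individuals, that reason for the waiver describes a safeguard that is not there. The protocol presents the trial as the first of its kind in autistic adults (3.1) and states that it has no sponsor (8.3.1), so the PI and the REB carry most of the safety decisions. The practical question is whether the next participant may be dosed while a serious event in an earlier one is still being assessed. No section answers it.

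The second reason for the waiver also sits badly with the rest of the document. It describes the *possible* outcomes as no worse than moderate. Section 3.2 names death, suicide attempt and hospital admission among the serious events to be evaluated, and 5.6 makes provision for psychosis that cannot be managed and for emergency calls in a hypertensive crisis.

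**Working it through.** **Scope of each provision.** The protocol states no figure for this point, so the first check is of the text.

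| Section | Provision | Acts on | Fixed trigger? | Cited in 8.7? |
|---|---|---|---|---|
| 4.7.1 | Five withdrawal reasons (pregnancy or contraception, non-compliance, AE or medical condition, disease progression, exclusion criterion) | One participant, then replaced | Not for the trial | Yes |
| 8.5 | Withdrawal after an SAE; urgent assessment for suicidality; removal by the PI | One participant | Not for the trial | Yes |
| 8.5 | PI review of AEs, reporting, regular team meetings | The trial, as review only | No; no pause or stop attached | Yes |
| 9.1 | Suspension or termination | The trial | No; discretionary | No |

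None of the stopping actions in the two cited sections acts on the trial.

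**Time available for a review.** Inputs: 20 participants recruited over 21 months (2.1, 3.1); V4 falls 7 to 10 days after V3 (6.2.1); follow-up runs to week 12, or 84 days, after V4. Assumptions: recruitment is evenly spaced, and a month is 30.44 days.

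- Spacing: 21 × 30.44 = 639.2 days; 639.2 / 20 = 31.96 days per participant.
- From one participant's V4 to the next participant's V3: 31.96 − 10 = 22.0 to 31.96 − 7 = 25.0 days.
- From one V3 to the next participant's V3: 32 days. If the SAE occurs at V3, that participant's own V4 is already barred by 8.5.
- Dosing of others in the 84 days after a V4: V3s at 22–25 and 54–57 days, V4s at 32 and 64 days. That is 4 doses in 2 participants.
- Share of days on which another participant is between V3 and V4: 7 / 31.96 = 21.9% to 10 / 31.96 = 31.3%.

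**Sensitivity.** Assume instead that dosing is compressed into 18 months, which is month 27 less the 9-month start-up in 3.1.

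- Spacing: 18 × 30.44 = 547.9 days; 547.9 / 20 = 27.4 days.
- V4 to next V3: 17.4 to 20.4 days.
- Within 84 days of a V4: V3s at 17–20, 45–48 and 72–75 days, V4s at 27, 55 and 82 days. That is 6 doses in 3 participants.
- Share of days with another participant between doses: 7 / 27.4 = 25.6% to 10 / 27.4 = 36.5%.

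This is not a worst case, because taper and follow-up must also fit into those 18 months. The protocol gives no SAE risk, so I attach no probability to an event.

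**The case against.** The strongest reply is that trial-level oversight is fuller than 8.7 conveys. The drug supplier receives AE and SAE reports within 24 hours (8.3.1). Health Canada receives reports of serious unexpected reactions within 7 or 15 days, followed by an assessment of their implications when fatal or life-threatening (8.3.3). The REB receives SAE reports (8.3.2) and reviews the trial at least yearly (12.1), and 9.1 lets the REB suspend it. A monitoring plan mentioned in 11.1 is not at hand and might contain a pause procedure. In an open-label trial of 20 at one site, where every event is seen at once, discretion is a defensible choice, and the day counts show that a review usually fits before the next dose.

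On the outcomes wording, 3.2 gives examples and 5.6 gives contingencies; neither is a prediction. Section 1.4 cites pooled trials in neurotypical people with no documented serious events.

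A strict rule could also stop the trial often. If a single related SAE triggers a pause, the chance of at least one pause among 20 participants is 1 − (1 − p)^20. For assumed risks p of 2%, 5%, 10% and 20%, that is 0.33, 0.64, 0.88 and 0.99.

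Much of this stands: the trial is not unsupervised, and the rule should be light. It does not remove the point. None of those reporting duties holds a dose, and 8.7 relies on none of them when it claims stopping rules. The claim is that the rules are in two named sections, and they are not. As for the wording, events that the protocol itself prepares for cannot be left out of what is possible, even if they are not anticipated.

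**Conclusion.** The concern holds. One of the three stated reasons for the waiver names a trial-level safeguard that the cited sections lack, and the only trial-level provision fixes no trigger and is not cited. This rests on the protocol text and needs no assumption.

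The practical size is moderate. With evenly spaced recruitment there are normally about three weeks or more before the next participant is dosed after a V4 event, or about two and a half weeks in the compressed case. The gap matters when recruitment bunches, when a serious event emerges during follow-up while two or three later participants are being dosed, or when someone else is already between the two doses. The point should be corrected by amendment; it does not undermine the trial.

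**What to change.** - **9.1:** add a pause-and-review rule agreed with the REB. For example, after a psilocybin-related SAE, or a suicide attempt after the first dose, no further participant is dosed until the PI has documented a review and notified the REB. Events during the pre-dose taper would not trigger it.
- **V4 window:** say how a participant between V3 and V4 is handled, for instance by allowing the 7–10 day window to be extended for this reason only.
- **8.7:** cite 9.1 for the trial-level rule and describe 4.7.1 and 8.5 as individual withdrawal and AE review. Change *possible* to *anticipated* outcomes, and acknowledge the serious risks that 3.2 and 5.6 provide for.

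The cost is an amendment to 8.7, 9.1 and the visit window, plus a short written review per triggering event. The drawback is an occasional delay for someone already off medication. A participant waiting for V3 repeats baseline once more than 7 days have passed since V2 (6.1.2.1). One between V3 and V4 has only 10 − 7 = 3 days of slack. Without the extension, a missed V4 could mean replacement, and 5.7 lists exactly 20 capsules of each strength. The extension is therefore part of the fix.
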